10.3.4 Protocol Deviations

A list of potential protocol deviations will be created and maintained for tracking by the Steering Committee. Each protocol violation report will include a description of the violation, the type of deviation that occurred, whether the date the deviation occurred, and whether the IRB was notified. The Steering Committee will review protocol deviations on an as needed basis to determine if subjects should continue in the study, the impact on the procedures, and the next steps for subject continuation. Examples of protocol violations include enrollment of an ineligible subject, randomization of an ineligible subject, failure to collect all screening tests, serious adverse events not reported in a timely fashion, breach of confidentiality, subject lost to follow-up, and visits outside of time window.

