6.1.2 Time between treatment weeks

- Intervention V4 to V5, V7 to V8 are 2-3-days apart
- Intervention V10 to V11, V12 to V13, V14 to V15 are 2-6-days apart
- Intervention V16-V17 is 6-10-days apart

Note: To allow for flexibility in participant scheduling due to events that may conflict with scheduled visits (e.g., acute illness), the total length of the intervention period (i.e., V2 T1 through V19 T18) can be extended by up to 30 days.

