6.2.6 Reasons for Early Termination

A subject would be discontinued from the study intervention if a medical condition develops that precludes the continuation of the treatment intervention. For participants who discontinue The VIGOR Study prior to completing all scheduled treatment sessions (regardless of the reason), we will make every attempt to obtain the outcome measurements. If the study participant is unwilling or unable to undergo the laboratory-based tests (e.g., difficulty tolerating the protocol, experienced an adverse event to a lab test) we will still attempt to obtain the clinical outcome

measures. In instances where an adverse event does occur, we will follow-up with participants until the event is resolved or until the IRB deems it unnecessary to continue to follow the participant.

If the participant complains of any sudden onset of muscle or joint pain, the current session will be terminated, and the Principal Investigator will be contacted to complete an assessment. If he is unavailable, one of the other clinicians on the study team will be contacted to provide a clinical assessment of the participant. They will then consult with the PI to assess if the participant should continue to stay on protocol. If an exclusion criterion is identified from the presenting signs and symptoms, the participant will then be withdrawn from the study. If the presenting signs and symptoms do not meet the exclusion criteria, the participant will be invited to return for their next scheduled visit when the sudden onset of symptoms has abated. Upon return, the PI or a clinician on the study team will again assess the participant and make a clinical judgement about their fitness to continue with the intervention. However, if the participant has a second episode of sudden onset of joint or muscle pain, they will be immediately withdrawn from the study.

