9.3 Definition of Populations

Intention to Treat Analysis (ITT): We will include all randomized study participants who have at least baseline endpoint assessments in our ITT analysis. The ITT analysis is our primary method for assessing outcomes, and how it is performed will be determined based on the pattern of missingness. If the missingness is deemed MCAR, the LOCF method will be used: simply the most recent valid observation will be "carried forward" to replace the subsequent missing observations. If the missingness is deemed MAR, missing observations will remain as missing, and

maximum likelihood estimation, the default estimation algorithm of LMER, will be used to estimate these observations. If the missingness is found to be MNAR, multiple-imputed data will be used to construct LMER models.

Per-Protocol Analysis (PPA): For the PPA we will exclude study participants who: 1) fail to attend 13 out of 18 treatment sessions; 2) develop an exclusionary medical condition while on study protocol, or 3) receive interventions outside of the Allowed (Section 5.3.1) during treatment. Finally, we will assess how comparable estimated parameters vary between ITT and PPA analyses.

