9.6 Data Analyses

We will analyze all outcome variables (pain, disability, pain/harm expectancy, and lumbar flexion) using linear mixed-effects (LME) models with treatment (Experimental, Control) as a between-subject fixed effect and time (pre-treatment, 1, 6, 12, 24, and 48 weeks) as a within-subject fixed effect. Given the expected findings, both linear and quadratic time effects will be tested in every model. We will also include demographic covariates (e.g., age, BMI) and potential confounders (e.g., radiating versus non radiating pain) as well as sex stratification in the LME models. Any variables that differ at baseline will be included in the statistical models as potential confounders.

Intention-to-treat analyses are commonly conducted to analyze randomized clinical trial data in the presence of missing values. While various imputation strategies have been proposed to estimate missing data, such as last observation carried forward, use of LME models to analyze longitudinal data renders these strategies largely unnecessary. We will also conduct equivalent per-protocol analyses that will include only successfully adhered participants (i.e., attending $\geq 70\%$ of gaming sessions).

Aim 1. Examine immediate clinical outcomes as a function of treatment. Relative to

the control group, participants in the experimental group will show greater reductions in pain and disability at post-treatment relative to pre-treatment baseline (Hypothesis 1).

To test Hypothesis 1, we will examine the Treatment by Time (baseline-post treatment) interaction in a LME model: a greater reduction in pain and disability in the experimental group than in the control group.

Aim 2. Examine potential mechanisms of pre- to post-treatment changes in clinical outcomes. Participants in the experimental group will exhibit greater pre- to post-treatment decreases in pain/harm expectancy and increases in lumbar flexion as compared to the control group (Hypothesis 2.1). Decreases in pain/harm expectancy and increases in lumbar flexion will be positively related to pre- to post-treatment reductions in pain and disability (Hypothesis 2.2).

Aim 3. Examine maintenance of treatment gains at 1-, 6-, 12-, 24-, and 48-weeks post-treatment. Relative to the control group, participants in the experimental group will continue to show lower levels of pain and disability at each time point as well as increased activity in their natural environment (Hypothesis 3).

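### The per-protocol rules in 9.3 and 9.6 differ, neither removes a participant who was ineligible at randomisation, and 10.3.4 does not separate stopping the intervention from stopping outcome follow-up

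*Combined protocol and SAP*

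**What the plan says.** **Deviations.** Section 10.3.4 states: "Examples of protocol violations include enrollment of an ineligible subject, randomization of an ineligible subject". The same list ends with "subject lost to follow-up, and visits outside of time window". On consequences it says: "The Steering Committee will review protocol deviations on an as needed basis to determine if subjects should continue in the study".

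**ITT set.** Section 9.3: "We will include all randomized study participants who have at least baseline endpoint assessments in our ITT analysis". This is the primary analysis.

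**Per-protocol set.** Section 9.3 removes three groups. The first is people who attend fewer than 13 of 18 sessions. The others are those who "2) develop an exclusionary medical condition while on study protocol, or 3) receive interventions outside of the Allowed" list in 5.3.1. Section 9.6 instead describes "equivalent per-protocol analyses that will include only successfully adhered participants", defined by attendance of at least 70%. Section 9.3 also plans to compare the ITT and per-protocol estimates.

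**Outcomes after stopping.** Section 6.2.6, repeated in section 8: "For participants who discontinue The VIGOR Study prior to completing all scheduled treatment sessions (regardless of the reason), we will make every attempt to obtain" outcome measurements. Section 6.2.5 promises all assessments for people who stop the intervention early.

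**Timing.** Section 6.1.1 sets gaps between sessions and windows for follow-up visits. Section 6.1.2 then says that "the total length of the intervention period (i.e., V2 T1 through V19 T18) can be extended by up to 30 days".

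**The concern.** A per-protocol analysis is meant to estimate the effect in people who belonged in the trial and were treated as planned. Here a participant who acquires an exclusionary condition in week 4 is removed, while one who had the same condition at entry, or who failed an inclusion criterion, is kept. Because 9.3 and 9.6 give different lists, two analysts following the plan could build different sets. The planned comparison of ITT and per-protocol estimates would also say nothing about eligibility errors, since both sets keep them.

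The second issue is what happens after a deviation review. The text speaks of continuing in the study, without saying whether treatment, outcome follow-up or both would end. Some listed violations, such as a late safety report or a confidentiality breach, may be staff errors that give no reason to stop collecting outcomes.

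**Working it through.** The plan gives no figure for this point, so the check is mainly a comparison of texts.

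**1. Do 9.3 and 9.6 agree?** On attendance, yes: 0.70 × 18 = 12.6, which rounds up to 13 sessions (13/18 = 72.2%). On the rest, no:

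| Reason for exclusion | 9.3 | 9.6 |
|---|---|---|
| Fewer than 13 of 18 sessions | yes | yes |
| Exclusionary condition arising on study | yes | not mentioned |
| Interventions outside 5.3.1 | yes | not mentioned |
| Ineligible at randomisation | not mentioned | not mentioned |

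**2. Can an ineligible person be randomised?** Section 4.1 requires a Tampa score above 36. The schedule in 6.1 lists the Tampa Scale at Visit 1 and Visits 20–24, not at Visit 0, and the Visit 0 list in 6.2.1 omits it. Section 4.3 randomises directly after the screening examination, and 6.1 marks randomisation at Visit 0. Section 6.2.2 places randomisation after the Visit 1 baseline assessments. On the 4.3 and 6.1 reading, allocation precedes the measurement of one eligibility criterion. Section 6.1.1 allows up to 7 days between screening and baseline.

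**3. Follow such a person through the rules.** Suppose the Visit 1 Tampa score is 36 or lower, all 18 sessions are attended and only allowed pain relief is used. Attendance passes. No exclusionary medical condition has developed. No outside intervention was received. The person stays in the per-protocol set under both sections.

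**4. How much could this matter?** Let *p* be the ineligible share of the per-protocol set, equal in both arms, and *h* the fraction of the eligible participants' effect that they obtain. The estimate relative to the effect in eligible participants is (1 − p) + p·h = 1 − p(1 − h). Both inputs are assumptions.

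| p | h = 0.5 | h = 0 |
|---|---|---|
| 0.05 | 0.975 | 0.95 |
| 0.20 | 0.90 | 0.80 |

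The estimate would be 2.5% to 20% too small. Section 9.2 plans falls of 30% and 10%, a difference of 20 percentage points; this would become 20 × 0.975 = 19.5 down to 20 × 0.80 = 16.0.

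**5. Who is covered by the outcome-collection promises?** Sections 6.2.6 and 8 cover people who leave before completing all treatment sessions. Section 6.2.5 covers early stopping of the intervention. Someone who has completed session 18 (Visit 19) and is then taken out after a deviation review falls under neither. Visit 20, which carries the Hypothesis 1 outcome, is due 7 ± 3 days after Visit 19, so the exposure is mainly Visits 21–24 (6 to 48 weeks).

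**6. Are delays inside the extension violations?** Gaps of 2–3, 2–6 and 6–10 days stand beside a 30-day extension of the whole intervention period. Section 10.3.4 lists visits outside the window as violations without saying which of the two defines the window.

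**The case against.** A reader might infer that deviation reviews can shrink the ITT set. The documents do not support this. Section 9.3 fixes membership by randomisation plus a baseline endpoint and has no exclusion for deviations or removal, and 10.3.4 defines no analysis set. Removal after baseline costs data, not membership. The one exception is narrow: a person randomised at Visit 0 and removed before the Visit 1 baseline would fail the baseline condition in 9.3.

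A reader might also infer a sizeable bias in the primary comparison. If 6 or 12 of 115 experimental participants were removed, the observed 20-point difference would compare with 30 × 109/115 − 10 = 18.4 or 30 × 103/115 − 10 = 16.9, an overstatement of 8.5% or 18.6%. But that requires every removal to be in one arm, every removed person to have had no change, and none of their outcomes to be collected. Nothing in the documents points to this. The investigators, statistician and data collectors are to stay blinded (5.2, 6.2.3, 9.2), outcomes are sought after early stopping, and 10.3.4 gives examples reviewed as needed, not automatic grounds for removal.

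On the per-protocol set, it is fair to say that the analysis is secondary, that 9.6 may be shorthand for 9.3 (5.3.1 supports the longer list), that screening includes a fear question and a physical examination, and that an ineligible person removed before session 13 leaves through the attendance rule. This limits the importance of the gap but does not close it. The fear question is a single agree-or-disagree item, not the Tampa score, and no rule removes an ineligible person who attends 13 or more sessions.

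**Conclusion.** Two points hold. First, the two per-protocol definitions differ, and neither deals with ineligibility at randomisation, which the plan itself calls a violation and which its own schedule makes possible. Secondly, 10.3.4 leaves open whether a deviation decision ends outcome follow-up, and the other sections do not cover a person removed after the last session.

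The size is unknown because the plan gives no rate of eligibility errors or removals. The 2.5–20% dilution rests on an assumed 5–20% ineligible share, equal between arms, with 0–50% of the effect; if ineligible participants responded as well as others, there would be no dilution. The follow-up gap mainly concerns the maintenance outcomes of Aim 3. It would reach the 1-week outcome only if removal fell between Visits 19 and 20. Neither point changes membership of the ITT set after baseline or calls for a different sample size.

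**What to change.** - **9.3:** add a fourth per-protocol exclusion: did not meet every criterion in 4.1 and 4.2 at randomisation. Have it judged by staff blind to arm, from data recorded before the first treatment. Visit 1 Tampa scores qualify, since 5.1 places the pre-treatment assessments before any exposure to the game.
- **9.6:** use the same four-part list, or refer to 9.3.
- **4.3, 6.1 and 6.2.2:** reconcile the timing of randomisation with the first Tampa measurement.
- **10.3.4:** state that a deviation decision concerns the study intervention, that participants removed for a deviation remain in the ITT set, and that their clinical outcomes are still sought as in 6.2.5, 6.2.6 and 8, including after the last session. Leave the safety withdrawal text in 6.2.6 and 7.1 unchanged.
- **10.3.4 with 6.1.1 and 6.1.2:** reconcile the out-of-window violation with the visit gaps and the 30-day extension.

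The cost is wording and a slightly smaller per-protocol set. Because the new exclusion uses only pre-treatment data judged blind, it should add no systematic imbalance between arms.

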10.3.5 Monitoring

The Steering Committee will be responsible for study monitoring. This committee will review and approve the study protocol prior to initiation of enrollment, will review SAEs and AEs at least twice annually and will be alerted to any interim concerns. Should any SAEs occur, they will be reported within 24 hours to the PIs.

11. PARTICIPANT RIGHTS AND CONFIDENTIALITY

11.1 Institutional Review Board (IRB) Review

This protocol and the informed consent document and any subsequent modifications will be reviewed and approved by the Virginia Commonwealth University IRB.

11.2 Informed Consent Forms

An initial screening will be conducted with all participants to describe the research study and determine their interest. For subjects who are interested in potentially volunteering for the study the study coordinator and/or principal investigators will meet with interested candidates. At this time individuals interested in participating can ask questions about the study. If they wish to be considered for the study they will then be asked to read and sign an informed consent document. A signed consent form will be obtained from each participant. The consent form will describe the purpose of the study, the procedures to be followed, and the risks and benefits of participation. A copy will be given to each participant and this fact will be documented in the participant's record. The principal investigators will work with the Virginia Commonwealth University IRB on an as needed basis to make provisions for special populations.

11.3 Participant Confidentiality

Data from self-report instruments and physical assessments are the primary source of research material. Measures will be taken to ensure the confidentiality of participant responses. Only those persons directly involved with conducting the study will be able to link the participant names with their information. All participants will be provided with a random ID number and no personal identifiers will be kept with the raw data. All informed consent documents will be filed separately so that there is no direct connection between participant names and any of their data. All hard copy data will be kept in locked filing cabinets. Physical and questionnaire data will be stored digitally using filenames corresponding to the participants ID number only. No identifying information will be used in any publications or presentations that result from this research. The code linking the random ID number with the participants name and contact information will be maintained through the follow-up period of the last enrolled subject (i.e., ~August 2023), at which point it will be destroyed.

All health-related data will be kept confidential by the investigators involved in this study. Specifically, only the investigators in the study will have access to patient data. Published or presented data will not identify patients in any way. Patients will not be audiotaped or videotaped. Data, forms, reports, and other records that leave the site will be identified only by a participant identification number (Participant ID, PID). All records will be kept in a locked file cabinet. All computer entry and networking programs will be done using PIDs only. Additionally, while every effort will be made to keep study-related information confidential, there may be circumstances where this information must be shared with: 1) Federal agencies, for example the Office of Human Research Protections, whose responsibility is to protect human

subjects in research; and 2) Representatives of Virginia Commonwealth University VCU, including the Institutional Review Board, a committee that oversees the research at VCU.

11.4 Study Discontinuation

The study may be discontinued at any time by the IRB, the NICHD, the OHRP, or other government agencies as part of their duties to ensure that research participants are protected.

12. COMMITTEES

Steering Committee: The VIGOR Study Steering Committee, which is charged with the overall governance of study conduct, consists of [name], PT, and [name]. The Steering Committee approves the final protocols and manuals of operations, supervises the overall execution of the trial, generates and approves study policies, considers modifications of the protocol and study operations, and plans and drafts study-related publications. The Steering Committee appoints and charges the subcommittees described below. All major scientific decisions are determined by consensus of the Steering Committee.

Medical Safety Committee: The VIGOR Study Medical Safety Committee, which consists of [name], PT, [name], [name], D.O. and Study Coordinator [name], reviews masked study data related to the overall safety of study participation, develops safety reports for the Data and Safety Monitoring Board, addresses IRB issues (related to participant safety) that may arise, reviews clinical practice-related issues and oversees the clinical safety of all study participants.

Data Safety and Monitoring Board: A Data Safety Monitoring Board (DSMB) that consists of an Independent Monitoring Committee IMC (IMC) monitors all aspects of the study, including those that require access to any blinded data.

Recruitment, Adherence, and Retention Committee: The VIGOR Study Recruitment, Adherence and Retention Committee ([name], PT, [name]., and members of the Study Coordination and Data Collection Team) refines and optimizes protocols and strategies for recruitment, adherence and retention of study participants. The Committee oversees recruitment progress, intervenes in cases of under-recruitment, and reports recruitment progress to the Steering Committee.

13. PUBLICATION OF RESEARCH FINDINGS

This study is governed by a Steering Committee and publication of the results of this trial will be governed by the policies and procedures developed by the Steering Committee.

